3. OBJECTIVE(S) AND ENDPOINT(S)

Objectives	Endpoints
Primary	

 To evaluate the efficacy of albiglutide liquid product as measured by glycated hemoglobin (HbA_{1c}) change from baseline at Week 26. 	
 Change from baseline in HbA_{1c} at Week 26
Secondary	

 To assess safety and tolerability of albiglutide specifically immunogenicity and ISRs. 	
 Adverse events (AEs) and serious AEs (SAEs), physical examinations, clinical laboratory evaluations, vital signs, and 12-lead electrocardiograms (ECGs). Anti-albiglutide antibody production and rates of ISRs over time.

 To evaluate the PD effect of albiglutide on fasting plasma glucose (FPG) change from baseline at Week 26. 	
 Change from baseline in FPG at Week 26

 To assess the PD effect of albiglutide over time 	
 Change from baseline in HbA_{1c} over time Change from baseline in FPG over time

 To evaluate trough PK concentrations of albiglutide following repeat dosing 	
 Trough concentrations of albiglutide

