5.5.3. Withdrawal from Study

[figure not shown]
Every effort should be made to keep subjects in the study. For subjects that choose to withdraw consent or are lost to follow up, the reason for not completing the study will be recorded in the subject's eCRF. If a subject withdraws from the study, he/she may request destruction of any samples taken, and the investigator must document this in the site study records.

Subjects who are withdrawn or discontinue active participation in the study will no longer receive the randomized study treatment. Immediately upon discontinuation from active participation in this study, these subjects should complete the assessments as per the end of treatment clinic visit and return for the post-treatment follow-up clinic visit 8 weeks later (Section 7.1). If a subject is unable or unwilling to return for the follow-up assessments, every effort will be made to follow-up with the subject.

Withdrawn subjects will not be replaced.

[figure not shown]

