6.9. Treatment after the End of the Study

Following completion of the Week 26 visit, eligible subjects who gave consent to participate in the extension study (Study 204682) will be treated as detailed in the extension study protocol. Those subjects who did not give consent to participate in the 26 week extension study will return to the study centre in 8 weeks for the post-treatment follow-up visit (Week 34 visit).

Investigational product will not be provided to subjects by GSK after the end of the study.

The investigator is responsible for ensuring that consideration has been given to the post-study care of the subject's medical condition, whether or not GSK is providing specific post-study treatment.

The half-life of albiglutide is approximately 5 days, and significant therapeutic concentrations can persist for 3 to 4 weeks after discontinuation. The choice of other medicinal products and dose selection should be considered accordingly, as adverse reactions may continue and efficacy may, at least partly, persist until albiglutide levels decline.

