7. STUDY ASSESSMENTS AND PROCEDURES

Protocol waivers or exemptions are not allowed with the exception of immediate safety concerns. Therefore, adherence to the study design requirements, including those specified in the Time and Events Table, are essential and required for study conduct.

This section lists the procedures and parameters of each planned study assessment. The exact timing of each assessment is listed in the Time and Events Table Section 7.1.

Supplementary study conduct information not mandated to be present in this protocol is provided in the accompanying SRM. The SRM will provide the site personnel with administrative and detailed technical information that does not impact subject safety.

Study visits between Baseline (Week 0) and End of treatment (Week 26) will have a visit window of ± 3 days and the follow-up visit (Week 34) will have a visit window of ± 7 days. If extraordinary events that make it impossible for subjects to complete a visit/dosing within the visit window (e.g., holidays, personal emergencies), the investigator should contact the medical monitor for advice.

If a subject misses a weekly scheduled visit for receiving albiglutide treatments, the albiglutide treatments should be administered as soon as possible within 3 days after the missed dose. Thereafter, subjects can resume dosing on their usual day of administration. If it is more than 3 days after the missed dose, the site staff should wait and administer at the subject's next regularly scheduled visit. If a subject misses 2 or more consecutive dosing, the investigator should contact the medical monitor to discuss options for helping assure better adherence. The medical monitor shall make a decision (on a case by case basis) on whether the subject should continue to receive investigation product.

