4. ANALYSIS POPULATIONS

Population	Definition / Criteria	Analyses Evaluated
Intent-To-Treat	
 Comprise of all randomized subjects who receive at least one dose of study treatment and have a baseline assessment. This population will be analysed according to randomly assigned treatment 	
 Efficacy
Safety	
 Comprise of all enrolled subjects who receive at least one dose of study treatment. This population will be analysed according to the treatment the subject actually received. 	
 Safety
Per-Protocol	
 Comprise of all randomized subjects who complete study procedures through Week 26 and are compliant with the protocol. This population will be analysed according to randomly assigned treatment. Protocol deviations that would exclude subjects from the PP population are defined in Section 4.1 (Protocol Deviations) and Appendix 1 (Protocol Deviation Management and Definition for Per-Protocol Population). 	
 Supportive analyses of the efficacy endpoints
Pharmacokinetic	
 Subjects in the Safety population for whom a pharmacokinetic sample is obtained and analysed. 	
 PK

NOTES :

- Please refer to [Appendix 14](#) List of Data Displays which details the population to be used for each displays being generated.

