8.3. Pharmacokinetic Analyses

Blood samples for the determination of albiglutide plasma concentrations will be obtained from all subjects before administration of study treatment at Week 12 and Week 26/early withdrawal. During visits where ECGs and vital sign measurements are required, blood samples will be collected after measurement of ECGs and vital signs.

Albiglutide concentrations will be summarized by treatment group at each visit using descriptive statistics (n, mean, SD, coefficient of variation [%], median, minimum, maximum, geometric mean and geometric mean coefficient of variation [%]).

Data will be summarized for the PK population and individual subject concentration data will be listed.

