8.3.1. Overview of Planned Analyses

The PK analyses will be based on the PK population.

[Table 6](#) provides an overview of the planned analyses, with further details of data displays being presented in [Appendix 14](#): List of Data Displays.

Table 6 Overview of Planned PK Analyses

Endpoints	Observed				Change from Baseline			
	Summary		Individual		Summary		Individual	
	T	F	F	L	T	F	F	L
Summary of [Analyte] [Matrix] Pharmacokinetic Concentration-Time Data by treatment group	Y		Y	Y				
Summary of [Analyte] Pharmacokinetic Urine Excretion Rate-Time Data by treatment group	Y		Y	Y				

NOTES :

- T = Table, F = Figure, L = Listing, Y = Yes display generated.
- Stats Analysis = Represents TFL related to any formal statistical analyses (i.e. modelling) conducted.
- Summary = Represents TFL related to any summaries (i.e. descriptive statistics) of the observed raw data.
- Individual = Represents FL related to any displays of individual subject observed raw data.

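### SAP 8.3 groups early-withdrawal PK samples with Week 26 and has no rule for which samples count as troughs (minor)

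*SAP*

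**What the plan says.** Protocol Section 3 names "Trough concentrations of albiglutide" as the secondary endpoint for exposure after repeat dosing. Protocol Table 4 schedules PK samples at Weeks 12 and 26 only, and its footnote calls them troughs taken before dosing. The last dose is at Week 25, so the Week 26 sample is nominally 7 days after it.

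SAP 8.3 states the second time point differently. Samples come from "all subjects before administration of study treatment at Week 12 and Week 26/early withdrawal", and "Albiglutide concentrations will be summarized by treatment group at each visit using descriptive statistics". The PK population in SAP Section 4 is "Subjects in the Safety population for whom a pharmacokinetic sample is obtained and analysed", with no condition on the sample itself.

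Early-withdrawal samples can arise because Protocol 5.5.3 says of subjects leaving the study that "these subjects should complete the assessments as per the end of treatment clinic visit". The end-of-treatment column of Table 4 includes the PK sample.

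SAP 11.3.2 slots safety and efficacy data to analysis visits, and SAP 11.3.4 gives windows for vital signs, ECG, laboratory tests, immunogenicity, weight, HbA1c and FPG. It gives none for PK.

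On dose timing, Protocol Section 7 says that after a missed visit "the albiglutide treatments should be administered as soon as possible within 3 days after the missed dose". If more than 3 days have passed, the dose waits for the next regular visit. Protocol 6.9 states: "The half-life of albiglutide is approximately 5 days".

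**The concern.** A trough has a meaning only relative to a dose and an interval. The SAP defines neither at sample level and puts two different situations under one visit label: a scheduled sample after 22 weeks on 50 mg, and a sample taken whenever a subject leaves. The second may come from the 30 mg period, before 50 mg steady state, or well after the last dose.

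Immunogenicity shows the contrast. SAP 8.2.3 also groups Week 26 with early withdrawal, but SAP 11.3.4 then assigns those records to analysis visits by study day and therapy phase. PK has no such step.

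At stake is a by-arm description of exposure to the two products in patients with type 2 diabetes. The geometric mean and the coefficient of variation, both reported, are sensitive to a few low values. If the rule is settled only after unblinding, any exclusion will look chosen.

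**Working it through.** **Inputs.** Half-life 5 days (Protocol 6.9); weekly dosing, 30 mg for 4 weeks then 50 mg (Protocol 6.3); 133 evaluable and about 150 randomised per arm, 13% loss (Protocol 9.2.1). Assumed: mono-exponential decline with superposition of doses, absorption ignored.

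**The plan's own figure.** For a margin of 0.4, SD 1, true difference 0 and one-sided 0.025, the noncentral t gives power 0.8993 at 132 per arm and 0.9015 at 133. So 133 is reproduced. 133/0.87 = 152.9, close to the stated 150. The sample size is not in dispute; it serves only to bound the number of early-withdrawal samples.

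**Ceiling on early-withdrawal samples.** 150 − 133 = 17 per arm, and 17/150 = 11.3%. Alternatively, 13% × 150 = 19.5 per arm. The ceiling is therefore 11-13% of Week 26 values. As labelled, it is none of the Week 12 values.

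**Are scheduled samples at steady state?** The on-schedule pre-dose level as a share of the 50 mg steady-state trough is 58.8% at Week 4, 84.4% at Week 5, 94.1% at Week 6, 99.2% at Week 8 and 99.98% at Week 12. Scheduled Week 12 and Week 26 samples are therefore at steady state. Dose level matters only for withdrawals before about Week 8.

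**Time since last dose.** After regular weekly dosing, the level relative to a 7-day trough is 2^((7 − t)/5):

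- t = 10 days: 0.66
- t = 14 days (one skipped dose): 0.38
- t = 15 days (latest liver-event PK sample in Protocol Appendix 3): 0.33
- t = 21 days: 0.14

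**Effect on the Week 26 summary.** With share p of samples at ratio r, the geometric mean is multiplied by r^p and the arithmetic mean by 1 − p(1 − r). The documents do not give days since last dose for early withdrawals, so t is an assumption. At 11.3% and 13%, the share is the ceiling; 5% and 2% are illustrative.

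| Share p | t = 10 d, geometric | t = 14 d, geometric | t = 14 d, arithmetic | t = 21 d, geometric |
|---|---|---|---|---|
| 13% | 0.95 | 0.88 | 0.92 | 0.78 |
| 11.3% | 0.95 | 0.90 | 0.93 | 0.80 |
| 5% | 0.98 | 0.95 | 0.97 | 0.91 |
| 2% | 0.99 | 0.98 | 0.99 | 0.96 |

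At 14 days the ceiling case is a fall of about 10-12% in the geometric mean.

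**Between arms.** If p and r are the same in both arms, r^p cancels and the ratio is unchanged. An assumed 5-percentage-point imbalance at 14 days moves it by 1 − 0.38^0.05, about 5%.

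**Visit windows.** Two consecutive visits at opposite edges of the ±3-day windows can be 1 or 13 days apart, and a dose given 3 days late leaves 4 days. The interval before the last dose then also departs from 7 days (10, 4 and 10 days respectively), so superposition is needed. In units of one dose, the 7-day steady-state trough is 0.379/(1 − 0.379) = 0.610 and the level just after dosing is 1.610.

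- 1 day: (1.610 × 2^(−10/5) + 1) × 2^(−1/5) / 0.610 = 2.00
- 4 days: (1.610 × 2^(−10/5) + 1) × 2^(−4/5) / 0.610 = 1.32
- 13 days: (1.610 × 2^(−4/5) + 1) × 2^(−13/5) / 0.610 = 0.52

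The extremes differ by about 3.8-fold. They are permitted, not expected; no frequency is given.

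**The case against.** The strongest reply is that few off-dose samples will exist. Subjects who stop the product but stay in the study follow Protocol Table 5, which has no PK row. Only those who leave the study have end-of-treatment assessments, and these are to be done immediately. Protocol 9.4.5.3 gives loss to follow-up or withdrawn consent as the reasons for leaving (SAP 11.6.3.3 adds investigator discretion), and subjects lost to follow-up give no sample. A sample weeks after the last dose mainly needs someone to stop the product, stay on, and later leave while still attending. This stands. It makes 11-13% a ceiling and the 21-day column an unlikely case.

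The PK data are also descriptive. The protocol plans no formal PK analysis, the median (little moved by contamination of this size) is reported, individual values are listed, and a separate bioequivalence study, 201287, addresses PK in healthy volunteers. This also stands and limits the importance.

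Finally, pooling is not stated outright, since the PK population defines subjects rather than samples. That is fair. But a single label combined with a summary at each visit makes pooling the natural reading, and without a slotting table the alternative is that handling is undefined.

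A reader might infer that many of the reported troughs are not 50 mg steady-state values. The documents do not support that: down-titration is prohibited, and scheduled samples are at steady state. A reader might also infer that injection-site reactions to the liquid product would bias the comparison through early stopping. Table 5 largely closes that route. Nor can it be shown that this is the only repeat-dose exposure comparison, because the extension protocol is not available.

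**Conclusion.** The point holds in limited form. The SAP lacks a sample-level rule for the trough endpoint and places early-withdrawal samples under the Week 26 label. At most about 11-13% of Week 26 values per arm may not be 50 mg steady-state troughs. A smaller share at either visit, which the documents do not allow one to estimate, may follow a skipped dose at about 0.38 of a 7-day trough.

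The 10-12% fall in the Week 26 geometric mean rests on four assumptions: the whole ceiling share yields a sample, all are drawn 14 days after the last dose, decline is mono-exponential with a 5-day half-life, and absorption is ignored. Any between-arm distortion requires an imbalance in such samples, and the primary HbA1c analysis does not use them. Severity is minor.

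**What to change.** In SAP 8.3, define the Week 12 and Week 26 trough summaries as using only scheduled samples (pre-dose at Week 12, end-of-treatment at Week 26) from subjects still on treatment whose last scheduled weekly dose was given. Require an interval since the last recorded dose that is fixed before unblinding and consistent with the protocol's ±3-day windows. A tight cut such as 7 ± 1 days is a preference and would discard protocol-compliant samples. Show early-withdrawal, off-interval and liver-event samples in the listing only, with actual days since last dose.

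The cost is SAP wording and programming, because dose dates and times are already recorded (Protocol 6.7, SAP 6.6). The downside is slightly fewer samples in the table: dropping the ceiling number of early withdrawals leaves about 130-133 Week 26 values per arm.

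Editorial only: in SAP Table 6, delete the row "Summary of [Analyte] Pharmacokinetic Urine Excretion Rate-Time Data by treatment group", since the protocol collects only blood for PK and the first row already covers concentrations. Add the PK table and listing to Appendix 14, which has neither.

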8.3.1. Overview of Planned Analyses

The PK analyses will be based on the PK population.

[Table 6](#) provides an overview of the planned analyses, with further details of data displays being presented in [Appendix 14](#): List of Data Displays.

Table 6 Overview of Planned PK Analyses

Endpoints	Observed				Change from Baseline			
	Summary		Individual		Summary		Individual	
	T	F	F	L	T	F	F	L
Summary of [Analyte] [Matrix] Pharmacokinetic Concentration-Time Data by treatment group	Y		Y	Y				
Summary of [Analyte] Pharmacokinetic Urine Excretion Rate-Time Data by treatment group	Y		Y	Y				

NOTES :

- T = Table, F = Figure, L = Listing, Y = Yes display generated.
- Stats Analysis = Represents TFL related to any formal statistical analyses (i.e. modelling) conducted.
- Summary = Represents TFL related to any summaries (i.e. descriptive statistics) of the observed raw data.
- Individual = Represents FL related to any displays of individual subject observed raw data.

8.4. Pharmacogenetic data analyses

Additional blood samples drawn for pharmacogenetic (PGx) analysis will be stored and may be analyzed in the future for exploratory study of variability in drug response because of hereditary factors in different populations. Whenever applicable, the details of these analyses will be described in a separate document. See the protocol for details about the Pharmacogenetics Analysis Plan.

9. OTHER STATISTICAL ANALYSES

Not applicable.

11.1. Appendix 1: Protocol Deviation Management and Definitions for Per Protocol Population

11.1.1. Exclusions from Per Protocol Population

Final list of protocol deviations that lead to exclusion from Per-Protocol population will be determined by the study team and populated here toward the end of the study.

A subject meeting any of the following criteria may be excluded from the Per Protocol population based on clinical judgement in a case-by-case basis. In addition, other deviations that may not fall under the following criteria may be excluded from the per protocol population based on a case by case basis:

Number	Protocol Deviation Description
01	Concomitant Medication 
 Subject took medication prohibited by protocol (SAFETY) Subject took medication prohibited by protocol (EFFICACY)
02	Study Treatment Compliance 
 Subject did not receive \geq 80% of planned medication
03	Inclusion Criteria and Exclusion Criteria 
 Subject enrolled but did not meet all protocol inclusion criteria at screening. Subject enrolled but met exclusion criteria at screening.
04	Study Treatment Admin/Dispense 
 Incorrect study medication kit and/or pen dispensed to subject.
05	ICF (Informed Consent Form) Process/Timing 
 ICF(s) not obtained prior to any study procedure. Site staff did not sign and/or date ICF. Genetic blood sample collected without subject consent. ICF re-consenting issues/delays Incorrect ICF used
06	Missing Endpoint Assessments 
 HbA1c blood sample not collected or insufficient/deficient at baseline or Week 26

11.1.2. Significant Protocol Deviation Rules

The Significant Protocol Deviation Rules Version 1.1, dated 21JUN2017, will be used to identify the significant protocol deviations. It is intended to categorize significant protocol deviations that are anticipated to occur in a study and to document study-specific requirements for cross-functional team review of these significant protocol deviations and other deviations that may occur in the study.

Part A of the Significant Protocol Deviation Plan is a list of the frequency that all deviations (protocol and GCP) will undergo review by a cross-functional team. (Review

should assess trending and appropriate categorization (both deviation type and significance)).

Part B is a list of each significant protocol deviation in the appropriate category and indicates the criterion that makes the deviation significant. Non-significant deviations should not be included.

This Significant PD Rules document should be updated when changes are identified (e.g., new deviation, re-classification of significance of a deviation). The revised document should describe changes in the Change History and appropriate version control should be applied.

11.2. Appendix 2: Time & Events

11.2.1. Protocol Defined Time & Events

Procedure	Visit Week ¹⁵ Visit Window	Treatment													
		1	2	3	4	5	6	7	8	9	10	11	12	13	14
		-2	0	1	2	3	4	5	6	7	8	9	10	11	12
		-14d	0d	±3d											
Informed consent	X														
Demography/medical history	X														
HIV, hepatitis B and C, amylase, lipase, alcohol and drug screen, TSH	X														
Inclusion/exclusion criteria review	X	X ¹													
Full (F) or brief (B) physical exam ²	F	B					B				B				
Height (H), Weigh (W), BMI	H, W, BMI						W				W				
12-lead ECG ³	X	X		X			X				X				
Vital signs ³	X	X	X	X	X	X	X	X	X	X	X	X	X	X	
Serum (S)/Urine (U) pregnancy test (WCBP)	S	U	U				U				U				
Clinical chemistry/hematology samples ⁴	X		X				X				X				
Lipids (including total cholesterol, LDL-C, HDL C, triglycerides, FFAs) ⁴	X														
Urinalysis	X														
HbA _{1c} ^{5, 8}	X	X	X				X				X			X	
eGFR	X		X								X				
Immunogenicity sample ⁶		X		X			X				X			X	
Genetic sample ⁷		X													
FPG ⁸		X	X	X	X	X	X	X	X	X	X	X	X	X	
PK samples ⁹														X	
Review AE/SAE, concomitant medication and hypoglycemia events	X	X	X	X	X	X	X	X	X	X	X	X	X	X	
Advice on diet and exercise ¹⁰		X	X	X	X	X	X	X	X	X	X	X	X	X	
Register visit into IVRS	X	X	X	X	X	X	X	X	X	X	X	X	X	X	

CONFIDENTIAL

200952

Randomization ¹¹		X														
Study Treatment		X	X	X	X	X	X	X	X	X	X	X	X	X	X	X

Procedure	Visit Week ¹⁵ Visit Window	Treatment													End of Treatment ^{12, 13}	Follow- up ¹⁴
		15	16	17	18	19	20	21	22	23	24	25	26	27	28	29
		13	14	15	16	17	18	19	20	21	22	23	24	25	26	34
		±3d	±3d	±3d	±3d	±3d	±3d	±3d	±3d	±3d	±3d	±3d	±3d	±3d	±3d	±7d
Informed consent																
Demography/medical history																
HIV, hepatitis B and C, amylase, lipase, alcohol and drug screen, TSH																
Inclusion/exclusion criteria review																
Full (F) or brief (B) physical exam ²	B			B				B						B	F	F
Height (H), Weigh (W), BMI	W			W				W						W	W	W
12-lead ECG ³															X	
Vital signs		X		X		X		X		X				X	X	X
Serum (S)/Urine (U) pregnancy test (WCBP)	U			U				U						U	S	U
Clinical chemistry/hematology samples ⁴				X											X	
Lipids (including total cholesterol, LDL-C, HDL C, triglycerides, FFAs) ⁴															X	X
Urinalysis															X	
HbA _{1c} ^{5, 8}				X				X							X	X
eGFR				X											X	X
Immunogenicity sample ⁶				X				X					X		X	X
Genetic sample ⁷																
FPG ⁸	X			X				X							X	X
PK samples ⁹															X	
Review AE/SAE, concomitant medication and hypoglycemia events	X	X	X	X	X	X	X	X	X	X	X	X	X	X	X	X
Advice on diet and exercise ¹⁰	X	X	X	X	X	X	X	X	X	X	X	X	X	X	X	
Register visit into IVRS	X	X	X	X	X	X	X	X	X	X	X	X	X	X	X	X
Randomization ¹¹																

Procedure	Visit	Treatment													End of Treatment ^{12, 13}	Follow-up ¹⁴	
		15	16	17	18	19	20	21	22	23	24	25	26	27	28	29	
		Week ¹⁵	13	14	15	16	17	18	19	20	21	22	23	24	25	26	34
		Visit Window	±3d	±3d	±7d												
Study Treatment	X	X	X	X	X	X	X	X	X	X	X	X	X	X			

TSH: thyroid stimulating hormone; BMI: body mass index; WCBP: women of child bearing potential; FFA: free fatty acids; LDL-c: low density lipoproteins cholesterol; HDL-c: high density lipoproteins cholesterol; d, day

1. **Before dosing**, the investigator must review **all** inclusion and exclusion criteria to confirm subject's eligibility. If a subject no longer meets all of the eligibility criteria (e.g., there is evidence of a new myocardial infarction (MI) on an ECG or ALT, etc. are out of range), **do not administer the study treatment** and contact the medical monitor to discuss how to proceed (e.g., to determine if repeat testing is warranted).
2. Details of full and brief physical examinations are provided in Protocol Section 7.4.3.
3. 12-lead ECGs will be obtained **before** measurement of vital signs and collection of blood samples for laboratory testing. Vital signs measurement will be taken before collection of blood samples. See Protocol Section 7.4.5.
4. Clinical chemistry and hematology assessments are described in Protocol Section 7.4.6.
5. Blood samples for HbA_{1c} should be collected before administration of study treatment.
6. Blood samples for immunogenicity are to be collected **before** study drug administration at the times specified in Protocol Section 7.1. A follow-up sample will be taken from each subject 8 weeks after the final dose of albiglutide is administered.
7. Blood sample for genetics can be collected at any time during the study after the genetics informed consent has been obtained and the subject has been randomly assigned to treatment group.
8. Subjects will have their FPG and HbA_{1c} levels evaluated to monitor for potential hyperglycemia.
9. PK samples (trough) will be obtained prior to dosing (Protocol Section 7.6).
10. Standard diabetic dietary and exercise advice will be provided at Visit 2 and reinforced through the end-of-treatment visit.
11. Once the HbA_{1c} results have been received from the central laboratory and all other eligibility criteria are met, study centre personnel will call the IVRS to obtain the subject's treatment assignment.
12. Subjects who discontinue study treatment should be handled as described in Protocol Section 5.5.
13. The end of treatment visit in Study 200952 is also Visit 1 of 204682 for those subjects continuing into the extension study.
14. Follow-up visit for subjects who have stopped investigational product (see Protocol Section 5.5), withdrawn from the study or who have completed the 26 week treatment period, but do not consent and/or are not eligible to participate in the 26 week extension study (Study 204682).
15. All visits will have a treatment window as in the table. Baseline (Week 0) serves as the reference point. Subjects will not be considered out of compliance if visit windows extend because of extraordinary events that make it impossible for subjects to complete a visit within the above window (e.g., holidays, vacations, personal emergencies). Determination of the maximum visit window deviation is at the discretion of the medical monitor

